FXI deficiency can be inherited autosomal recessive and autosomal dominant[33]. It is the mildest of the rare bleeding disorders, with bruising, epistaxis and menorrhagia as the most common manifestations [5, 14]. The correlation between coagulation factor activity and clinical bleeding is poor [19]. This may (in part) be explained by the coexistence of other coagulation disorders. In some patients with severe FXI deficiency a combined FXI and von Willebrand disease has been reported, leading to a more severe bleeding tendency [16]. Excessive bleeding has also been reported in heterozygous individuals. A single study from the United Kingdom showed that 48% of heterozygous individuals had a bleeding tendency, [34]. Comparison of histories between partially deficient and non-deficient individuals demonstrated a higher prevalence of menstrual problems (41% vs. 18%), an increase in significant bruising (38% vs. 14%), an increased likelihood of excessive bleeding after dental extractions (51% vs. 9%), and an increased number of blood transfusions after interventions (56% vs. 0%). Bleeding in heterozygous individuals has also been described to be related to genetically compound disease, other factor deficiencies or defects, or platelet dysfunction in some cases [12-18].

FXIII deficiency

FXIII deficiency is an autosomal recessive disorder. This deficiency has serious clinical consequences. Of 112 cases reported in the literature from 1978 23 individuals (21%) had died of bleeding, and notably 22 of these were relatives of established cases, for whom the diagnosis was highly likely but could not be proven [35]. Umbilical cord bleeding was seen in

73-80% of cases and may be delayed up to 19 days after birth; surgical bleeding in 84%; superficial bruising in 58-60%; subcutaneous haematomas in 55-58%; intracranial bleeding in 25-30%; mouth and gum bleeding 30-48%; muscle bleeding 27%; and joint bleeding in 24-55% of reported cases [35, 36]. Habitual abortions (50% of women) and menorrhagia (35% of women) are also frequent. Women with a complete deficiency are unable to carry a pregnancy to term [36, 37]. Impaired wound healing is another symptom patients may experience [37]. It is currently not clear if people with a heterozygous factor XIII deficiency have an increased bleeding risk[38].

Alpha-2-antiplasmin deficiency

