Alpha-2-antiplasmin deficiency is an autosomal recessive disorder. Most patients with alpha-2-antiplasmin deficiency experience severe bleeding appearing during childhood. Umbilical cord bleeding has been described, as well as intramedullary haemorrhage into the diaphyses of long bones. Heterozygous individuals can be asymptomatic or have milder symptoms, mostly occurring after trauma, surgery or dental extractions. With age the plasma levels decrease which can lead to increase in symptoms [6, 7].

Plasminogen activator inhibitor deficiency

PAI-1 deficiency is an autosomal recessive disorder. The bleeding symptoms in PAI-1 deficiency are usually mild to moderate. Bleeding after surgery is a common complication as well as abnormal bleeding after dental procedures. Most bleeding episodes are post-traumatic. Epistaxis has also been described as well as menorrhagia, sometimes leading to iron deficiency anaemia or even the need for transfusion [8, 9].

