5. STUDY POPULATION

5.1. Population (base)

Based on the prevalence in the general population of 1:500,000 to 1 per 2 million persons [1, 2], and a total population of 17 million, there should be 129 to 145 individuals with a homozygous rare bleeding disorder in the Netherlands. This could be higher taking into account the possible influences of high-risk populations such as Ashkenazi or Iraqi Jews with high FXI deficiency rates. To date, 337 patients with a rare bleeding disorder are known to the eight Dutch centers that treat such patients. Approximately one third of these patients are homozygous; and around two thirds are heterozygous individuals.¹

All known homozygous and heterozygous patients with a rare bleeding disorder will be invited to participate.

Heterozygous prevalence in the Netherlands have not been evaluated, but can be calculated according to the Hardy-Weinberg principle² to be 93,000 to 99,000 persons, or 0.55% to 0.58% of the Dutch population (5.5 to 5.8 per 1,000 persons) for all rare bleeding disorders combined. Though the estimated number of heterozygous persons in the Netherlands is much higher than the number of persons known to one of the eight treating centers (~179 heterozygous patients³), we expect that the individuals with a known heterozygosity represent a subset with a more severe clinical presentation, who are therefore of interest to our research question.

Characteristics of the Dutch source population

The characteristics of the Dutch population (both homozygous and heterozygous) are largely unknown and are a part of this study. Numbers of known patients per rare bleeding disorder are presented in

[Table 3](#)

[Table 3.](#)

¹ A quick inventory in the Radboud university medical center learned that two thirds of patients were heterozygous individuals whereas one third were homozygous individuals. Based on an inventory of 63 medical files performed on July 8, 2016: 65% missing information, 24% heterozygosity, 11% homozygosity

² The Hardy-Weinberg proportion stipulates that for a single locus with two alleles denoted 'A' and 'a' with population frequencies p and q respectively, the expected genotype frequencies are p² for the AA homozygous individuals, q² for the aa homozygous individuals, and 2pq for the heterozygous individuals. The sum of these frequencies must be 1, thus p² + 2pq + q² = 1 and p + q=1.

Table 3 Prevalence of rare bleeding disorders in the Netherlands

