5.2. Inclusion criteria

In order to be eligible to participate in this study, a subject must meet all of the following criteria:

- Established homozygous or known heterozygous rare bleeding disorder due to deficiency or dysfunction of fibrin, FII, FV, FV & FVIII, FVII, FX, FXI, FXIII, alpha-2-antiplasmin and PAI-1 ;
- Age 1 year and older;

- For patients ≥ 16 years old; written informed consent.
- For patients 12-16 years old; written informed consent from both the patient and their parents/legal guardian(s).
- For patients <12 years old; written informed consent from their parents/legal guardian(s).

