7. STATISTICAL ANALYSIS

Statistical analysis will be performed by the research team at Radboud university medical center. First we describe the general outline of statistical analyses, then we discuss specific statistical procedures for the primary and secondary objectives separately, if appropriate.

In general, continuous variables will be described using standard summary statistics (e.g. mean, medians and corresponding 95% confidence interval (CI),); categorical variables will be described using frequencies and percentages with their 95% CIs. Group differences will be determined using analysis of variance (ANOVA) or Student's t-test for continuous variables and Fisher's exact test for categorical variables (Fisher-Freeman-Halton exact test for variables with more than two categories). Non-parametric tests will be used for results with non-normal distributions. Two-sided p-values smaller than 0.05 will be considered statistically significant. Because of the explorative character of this study no correction for multiple testing will be applied.

The following parameters will be categorized when appropriate:

- Bleeding score (ISTH-BAT): ≥ 5 abnormal for women, ≥ 3 abnormal for men
- Clinical bleeding severity [19]:
 - Asymptomatic: no documented bleeding episodes
 - Grade I bleeding: bleeding that occurred after trauma or drug ingestion (antiplatelet or anticoagulation therapy)
 - Grade II bleeding: spontaneous minor bleeding (bruising, ecchymoses, minor wounds, oral cavity bleeding, epistaxis and menorrhagia)
 - Grade III bleeding: spontaneous major bleeding (intramuscular haematomas requiring hospitalizations, haemarthrosis, bleeding of the central nervous system, the umbilical cord or the gastrointestinal tract)

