8.4. Benefits and risks assessment, group relatedness

There is a possible minor bleeding risk for people participating in this study connected to collection of blood. However, this is a very minor risk considering the experience of patients and nurses. Blood of patients having RBDs is routinely tested during regular visits to treatment centers and risks associated to blood sampling are considered to be negligible.

Patients will not directly benefit from participating in this study but in the long term this study contributes to our knowledge of the rare bleeding disorders and will increase awareness of these disorders amongst health care workers, as such improving diagnostics and care.

Since the population of patients having RBDs is very small, it is important to include all patients, also minors (children <18 years), in the study (around one third of known patients are minors). Therefore this study may be regarded as group-related.

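### The severity grade scores a patient with no haemostatic challenge and no spontaneous bleed the same as one who was challenged and did not bleed

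*Combined protocol and SAP*

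**What the plan says.** Section 7 grades clinical bleeding severity in four levels, taken from reference 19. The levels that bear on this point are:

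- Lowest level (called grade 0 below): "Asymptomatic: no documented bleeding episodes".
- Next level: "Grade I bleeding: bleeding that occurred after trauma or drug ingestion (antiplatelet or anticoagulation therapy". Surgery, dental extraction and delivery are not named.
- Grade II starts with "Grade II bleeding: spontaneous minor bleeding", and Grade III is spontaneous major bleeding. Neither needs a challenge.

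The inclusion criteria (section 5.2) admit patients at "Age 1 year and older", and section 8.4 says that "around one third of known patients are minors".

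Section 7.1 uses clinical bleeding severity as a continuous independent variable in the regression on factor activity level, and as one of the possible independent variables for quality of life. Both regressions adjust for age, sex and an open list of other covariates; challenge history is not named. For validating the factor levels at which patients stay free of symptoms, section 7.1 gives descriptive statistics only. Section 3 lists that objective as secondary.

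**The concern.** Grade 0 contains two kinds of patient: those who met a haemostatic challenge and did not bleed, and those who have not yet met one and have had no spontaneous bleed. Only the first kind shows that a given factor level was enough under challenge. The contrast between grade 0 and Grade I therefore mixes bleeding tendency with opportunity to bleed.

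The protocol's background (section 1.2) shows why opportunity matters here. Of PAI-1 deficiency it says "Most bleeding episodes are post-traumatic". It describes symptoms in alpha-2-antiplasmin heterozygotes as mostly provoked. For partial FXI deficiency it reports excessive bleeding after dental extraction in 51% against 9% of non-deficient people. Children, who can enter from age 1, are the obvious group with little exposure so far.

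Two results are at stake. In the level-severity regression, unchallenged patients with low levels sit in the lowest grade and weaken the association. In the analysis of symptom-free levels, they add to the apparent number of people who do well at a low level.

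**Working it through.** The plan states no sample size, power or error rate that depends on this definition, so there is no figure to reproduce. The check is of direction and possible size.

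**Inputs from the protocol**
- Known patients: 337 (section 5.1). Minors: about one third (section 8.4), so 337/3 ≈ 112.
- Expected response: 70% (section 5.1), so 0.70 × 337 ≈ 236 participants, of whom about 79 are minors if response is the same in both groups.
- Excessive bleeding after dental extraction in partial FXI deficiency: 51% (section 1.2).

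**Assumed inputs (not in the documents)**
- Unchallenged: 60% of minors and 10% of adults.
- b = 60%: bleeding of any kind among challenged patients.
- s: spontaneous bleeding among unchallenged patients, set to 0% and then 30%.

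**Step 1. Unchallenged share**
u = 0.60 × 1/3 + 0.10 × 2/3 = 0.267, or 27%.

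**Step 2. Share graded asymptomatic**
Share read = u(1 − s) + (1 − u)(1 − b). Share among challenged patients = 1 − b = 40%. The difference between them is u(b − s).
- s = 0%: 0.267 + 0.733 × 0.40 = 56% against 40%. Of those graded asymptomatic, 0.267/0.56 = 48% were never challenged.
- s = 30%: 0.267 × 0.70 + 0.733 × 0.40 = 0.187 + 0.293 = 48% against 40%. The gap halves, from 16 to 8 points.

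The gap is zero if s = b, that is, if being challenged adds nothing to the chance of a recorded bleed.

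**Step 3. Range with s = 0%**
- Minors 40%, adults 5%, b = 40%: u = 0.167; 0.167 + 0.833 × 0.60 = 67% against 60%.
- Minors 80%, adults 20%, b = 80%: u = 0.40; 0.40 + 0.60 × 0.20 = 52% against 20%.

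**Step 4. The protocol's own 51% as b, with s = 0%**
The share among challenged patients is 49%. It reads 54% at u = 10%, 59% at u = 20% and 66% at u = one third. Two groups with the same risk under challenge also look different if exposure differs: with 60% and 10% unchallenged, the shares read 0.60 + 0.40 × 0.49 = 80% and 0.10 + 0.90 × 0.49 = 54%.

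**Step 5. Two ways to correct, with u = 27%, b = 60%, s = 30%**
- Drop only unchallenged non-bleeders: 0.293/(1 − 0.187) = 0.293/0.813 = 36%. This undershoots 40%, because unchallenged spontaneous bleeders stay in Grades II and III.
- Drop all unchallenged patients, whatever their grade: 0.293/0.733 = 40%.

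**The case against.** Several arguments on the other side stand, and they set the limits of the point.

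- A reader might infer that every unchallenged patient is graded asymptomatic. The grading does not support that: spontaneous bleeds reach Grade II or III without a challenge. Section 1.2 names bruising, nosebleeds and heavy menstrual bleeding as the most common FXI manifestations, and section 7 lists all three under Grade II. Nosebleeds and heavy menstrual bleeding also occur in PAI-1 deficiency. So it would be wrong to count all FXI and PAI-1 patients as affected.
- A reader might infer that the study will make low levels look safe. The net direction is not shown. Section 1.2 warns that data from clinical records may overstate severity, and section 5.1 expects known heterozygotes to be the more severe ones. Both act the other way, and neither is quantified.
- Age adjustment covers part of the problem in children. It remains a proxy: it does not identify unchallenged adults, and the analysis of symptom-free levels has no adjustment at all. The documents do not state the functional form of the age term.
- Challenge history may already be collected. Table 4 lists bleeding scores, medical history and pregnancies, and the questionnaires are in separate documents not seen here. The gap shown is in the definition and the analysis, not necessarily in the data.
- Reference 19 is the source of both the grading and the symptom-free levels to be validated. Replacing the grade in the main analysis would break that comparison.
- Section 7.1 does not say that the four-level grade decides who is free of symptoms. It is, however, the only definition of an asymptomatic patient that the protocol gives.

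**Conclusion.** The point holds as a cheap improvement. The grade cannot separate patients who were challenged and did not bleed from patients who were never challenged and had no spontaneous bleed, and nothing else in the protocol does so beyond the age term in the regressions. It matters mainly for mild or heterozygous disease and for children.

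Taken alone, the mechanism inflates the symptom-free share at a given level whenever a challenge adds to the chance of a recorded bleed. The figures of 56% or 48% against 40% are illustrations: the unchallenged share, the bleeding risk under challenge and the spontaneous bleeding risk are all assumed. The documents support neither a specific size nor a statement about the net bias once selection into the clinics is taken into account.

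**What to change.** 1. Keep the reference 19 grade as the main definition, so that results stay comparable with the levels being validated.
2. At the planned clinical interview, record whether the patient has had at least one defined challenge (surgery, dental extraction, delivery or trauma, with trauma defined in advance) and whether it was covered by prophylactic or haemostatic treatment. If menstruation is to count as a challenge, align the wording with the Grade II entry for menorrhagia.
3. Report grade 0 in two parts: 'challenged, no bleed' and 'not yet challenged'.
4. Repeat the level-severity, quality-of-life and symptom-free-level analyses in challenged patients only. Apply the restriction to all grades, because applying it to grade 0 alone biases the share the other way (36% against 40% in the illustration).

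The cost is one interview item (less if the questionnaires already hold it), a few lines in section 7, a little more analysis, and a smaller group in the restricted analysis. No extra visit or blood is needed. The study has no follow-up (section 6.5), so the item is best collected at the visit.

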7.1. Primary objectives

- *Describe the epidemiology, clinical presentation, bleeding score, bleeding episodes, quality of life, laboratory parameters, genetics and treatment of homozygous and known heterozygous individuals (of all ages) with rare bleeding disorders (disorders of fibrinogen, FII, FV, FV & VIII, FVII, FX, FXI, FXIII and alpha-2-antiplasmin and PAI-1 deficiency) in the Netherlands;*

We will use descriptive statistics using means, SD and medians. Interquartile ranges will be used when appropriate. Prevalence will be reported with 95% confidence intervals.

- *Examine the relationship between clinical and laboratory presentation (clinical and laboratory phenotype), and between phenotypes and genetics (genotype);*

Descriptive statistics will be used. Regression analysis will be used to determine the association between coagulation factor activity level (dependent variable) and clinical

bleeding severity as a continuous variable (independent variable), with adjustment for age at data collection, sex, etcetera.

- *Examine the relationship between quality of life, phenotype and genotype;*
Descriptive statistics will be used. Regression analysis will be used to determine the association between quality of life (dependent variable) and clinical bleeding severity or coagulation factor activity level as a continuous variable (independent variable), with adjustment for age at data collection, sex, etcetera.
- *Validate the established factor activity levels for patients to remain without symptoms.*
Descriptive statistics will be used.

7.2. Secondary objectives

- *Compare the clinical presentation, bleeding score, quality of life and laboratory parameters of individuals with a rare bleeding disorder (disorders of fibrinogen, FII, FV, FV & VIII, FVII, FX, FXI, FXIII and alpha-2-antiplasmin and PAI-1 deficiency) to those of individuals with haemophilia A or B (HiN study data will be shared)*
Descriptive statistics will be used. Group differences will be determined using the statistics as described in Statistical Analysis above.
- *Establish a firm base for a future Dutch registry for homozygous and known heterozygous individuals with rare bleeding disorders (disorders of fibrinogen, FII, FV, FV & FVIII, FVII, FX, FXI, d FXIII and alpha-2-antiplasmin and PAI-1 deficiency):*
 - *To develop a standard set of patient-reported, clinical and administrative data to be collected on a regular basis*

No statistics are involved in this objective.

- *Liaise with the pro-RBDD study, a similar study in Italy, to work towards a pan-European study linking phenotype to genotype in individuals with rare bleeding disorders*
No statistics are involved in this objective.
- *To assess if the NHA can distinguish mild clinical phenotypes in patients with similar factor activity levels*
We will calculate diagnostic accuracy comparing NHA to ISTH BAT.
- *To evaluate the usefulness of saliva coagulation biomarker tests in the management of patients with a rare bleeding disorder*
Descriptive statistics will be used. Regression analysis will be used to determine the association between saliva biomarker tests (dependent variable) and coagulation factor activity level as a continuous variable (independent variable), with adjustment for age at data collection, sex, etcetera.

- *To evaluate the use of WES in explaining differences in bleeding tendency.*
Descriptive statistics will be used.
- *To examine whether age-dependent laboratory changes in factor concentrations and fibrinolysis occur individuals with rare bleeding disorders? And if so, do they influence clinical phenotype?*
Descriptive statistics will be used. Regression analysis will be used to determine the association between age (dependent variable) and coagulation factor activity level as a continuous variable (independent variable), with adjustment for age at data collection, sex, etcetera.
- *To evaluate if patients with rare bleeding disorders are protected from arterial thrombosis*
Descriptive statistics for continuous variables will be presented as medians and 25–75% interquartile ranges (IQR), because data are not normally distributed. For comparison of proportions, the chi-squared test or the Fisher's exact test will be used. Wilcoxon tests will be performed for comparison of age and coagulation factor levels between groups. Standardized morbidity ratios (SMR) will be calculated to estimate the rate of overall arterial thrombosis and of coronary heart disease, acute myocardial infarction and ischemic stroke separately in patients relative to that of the reference population adjusted for age and sex.

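### The comparison with haemophilia A and B has no planned adjustment for sex or age, so a difference in sex mix can create or hide a difference in bleeding severity

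*Combined protocol and SAP*

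**What the plan says.** Section 7.2 plans to compare clinical presentation, bleeding score, quality of life and laboratory parameters with those of people with haemophilia A or B, using shared HiN data. Beyond descriptive statistics, the method is one sentence: "Group differences will be determined using the statistics as described in Statistical Analysis above". Section 7 offers ANOVA or the t-test for continuous variables and Fisher's exact test for categorical ones, and adds: "Non-parametric tests will be used for results with non-normal distributions". For this comparison neither section names a covariate, stratum, matching or restriction.

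Elsewhere the plan does account for sex and age:

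- Section 7 sets sex-specific limits: "Bleeding score (ISTH-BAT): ≥ 5 abnormal for women, ≥ 3 abnormal for men". It also counts menorrhagia as Grade II bleeding.
- Both regressions in section 7.1 are planned "with adjustment for age at data collection, sex, etcetera", and the two in section 7.2 carry the same clause.
- The standardized morbidity ratio for arterial thrombosis is "relative to that of the reference population adjusted for age and sex".

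Section 2 gives the motive: rare disorders are often ranked as less severe than haemophilia, and shared questionnaires would allow the two to be compared directly.

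**The concern.** Table 2 places every rare-disorder gene on a numbered chromosome, so both sexes should be well represented among these patients. If the haemophilia cohort is mostly male, a crude difference in the continuous bleeding score or in severity grade contains a sex effect as well as a disease effect. It can make the rare disorders look worse than haemophilia when they are not, or cancel a truly higher haemophilia score. The crude result would still describe the two patient groups correctly. It could not by itself answer the severity question raised in section 2.

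Age is a second possible confounder. Section 1.7 says that several clotting-factor concentrations rise with age in healthy people, which bears on the laboratory comparison. The age effect is not quantified here.

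**Working it through.** The plan gives no sample size, effect size or power for this comparison, so there is no figure to reproduce. The calculation below is an illustration.

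**Inputs from the protocol.** 337 known patients (Table 3) and 70% expected response (section 5.1) give 337 × 0.70 = 236. Section 8.4 says "around one third of known patients are minors", and Table 4 lists a separate bleeding tool (iCHEC) for children, so adults number about 236 × 2/3 = 157. For FVII alone: 92 × 0.70 × 2/3 = 43. The test is two-sided at 5%.

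**Assumptions, not in the documents.** 50% women among rare-disorder patients and 2%-10% in haemophilia; 300, 600 or 1,000 haemophilia patients; score SD 4 or 6; women score 0.2 to 2 points higher than men. The upper value equals the distance between the plan's two cut-offs, which is not a measured mean difference. The menorrhagia rates in section 1.2 do not fix the gap: they come partly from severe or homozygous series, while about two thirds of Dutch patients are said to be heterozygous.

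**Formulas.** Spurious difference = sex gap × (share of women in rare disorders − share in haemophilia). SE = SD × √(1/n1 + 1/n2). Rejection probability = Φ(difference/SE − 1.96) + Φ(−difference/SE − 1.96).

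**Worked end points, 2-point gap, no within-sex difference.**
- Low: 2 × (0.50 − 0.10) = 0.80; SE = 6 × √(1/157 + 1/300) = 0.591; rejection 27%.
- High: 2 × (0.50 − 0.02) = 0.96; SE = 4 × √(1/157 + 1/1,000) = 0.343; rejection 80%.

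**All gaps, 157 adults.** For masking, haemophilia is truly 1 point higher within each sex, so the expected crude difference is 1 − gap × 0.48 or 0.40.

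| Sex gap (points) | Spurious difference | False rejection, crude | Expected crude difference (masking) | Crude power (masking) |
|---|---|---|---|---|
| 0.2 | 0.08-0.10 | 5%-6% | 0.90-0.92 | 33%-76% |
| 0.5 | 0.20-0.24 | 6%-11% | 0.76-0.80 | 25%-64% |
| 1 | 0.40-0.48 | 10%-29% | 0.52-0.60 | 14%-42% |
| 2 | 0.80-0.96 | 27%-80% | 0.04-0.20 | 5%-9% |

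Sex-adjusted regression has 28%-77% power in the masking scenario. Its SE is SD/√(Im + If), with Im = 1/(1/m1 + 1/m2) for men and If = 1/(1/f1 + 1/f2) for women. At a 0.2-point gap it gains nothing.

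**Sensitivity.** With 25% women in haemophilia, false rejection is 7%-11% at 1 point and 14%-31% at 2. With equal sex mix it is 5%. For FVII alone (43 adults, 2%-10% women in haemophilia) it is 7%-12% at 1 point and 13%-34% at 2.

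**Do the sex-specific cut-offs solve it?** Only in part. Scores were simulated for 157 versus 500 patients from negative binomial distributions (men's mean/SD 4/4, 6/4, 6/6 or 8/6; three ways of raising women's scores; 500 runs per setting). They were classified with the plan's cut-offs and compared by Fisher's exact test. False rejection was 8%-50% at a 1-point gap and 3%-25% at 2 points. The mean difference in the share abnormal (rare disorders minus haemophilia) was −8 to −3 percentage points at 1 point, so the rare disorders looked milder, and −5 to +2 at 2 points. Linear regression on group and sex with robust SEs rejected in 4%-7% of the same simulations.

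No figure is claimed for severity grade, quality of life or laboratory parameters.

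**The case against.** **The aim may be purely descriptive.** Sections 3 and 7.2 speak of comparing clinical presentation, and a crude contrast does that. Menorrhagia is also partly an effect of the disease: section 1.2 reports menstrual problems in 41% versus 18% for partial FXI deficiency. This stands, and it is why the crude comparison should be kept. It does not cover a conclusion about severity, which section 2 invites.

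**The larger figures need pooling and a large sex gap.** The plan does not say whether the rare disorders are pooled. At a 1-point gap, false rejection by single disorder is about 7%-12% for FVII and FXI (88 × 0.70 × 2/3 = 41 adults) and 5%-8% for the other eight. Neither cohort's sex mix, the haemophilia sample size, the SD nor the sex gap is documented. This limits the size of the claim, not the omission. For age in particular, nothing in the documents shows that the cohorts differ.

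**Adjustment is fragile with few women.** At 2% women, 300-1,000 haemophilia patients include only 6-20 women, and a model without interaction assumes the same group difference in both sexes. This is fair and calls for a males-only supporting analysis. Differences in zygosity and ascertainment would also remain after adjustment.

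**The non-parametric option is no defence.** With skewed scores and 2% women in haemophilia, a Wilcoxon test showed similar inflation.

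**Conclusion.** The concern holds as a conditional one. The plan names unadjusted tests for this comparison while it treats bleeding as sex-dependent and accounts for age and sex in its other modelled analyses. If the sex mix differs, the crude result can create or hide a difference in severity. The effect could be negligible (small sex gap or similar sex mix) or large (pooled disorders, 2-point gap, nearly all-male haemophilia cohort); the documents do not allow a choice between these. Confidence is medium because the sizes rest on assumptions. The objective is secondary, the study is declared explorative, and the primary objectives are not affected, so the change is advisable rather than essential.

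**What to change.** - Keep the crude comparison as description, and report the sex and age mix of both groups beside it.
- Base any statement on relative severity on a regression of the outcome on group, adjusted for sex and age as in the other objectives.
- State whether the rare disorders are pooled. Fit the model to the pooled group and to single disorders where numbers allow. Stay descriptive for the smallest: at 70% response, all ages, FV & FVIII 4 × 0.70 ≈ 3, FII 9 × 0.70 ≈ 6, FX 10 × 0.70 = 7.
- Add a males-only comparison as a supporting analysis if the haemophilia data contain few women.
- Analyse adults and children separately where the instruments differ (Table 4).
- Obtain age and sex with the shared haemophilia data.

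The cost is SAP wording and slightly more analysis; sex and date of birth are already collected for RBiN participants (Table 4). Precision falls somewhat. Under the assumptions above, for 157 adults the 95% CI half-width is 0.73-1.43 points sex-adjusted against 0.67-1.16 crude (8%-25% wider, setting by setting), and 0.92-1.51 for males only.
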